The AirFit F40 is a minimal contact FFM manufactured by ResMed (San Diego, CA) that rests softly and securely under the patients nose and is designed to let patients sleep in any position and move freely throughout the night. The mask consists of three cushion sizes and three headgear sizes. Headgear adjustments can be made with magnetic clips that easily snap on and off.

The AirFit F40 MCFFM is for single-patient reuse in the home environment. The mask is intended to be used on patients weighing more than 66lbs (30kg), who have been prescribed non-invasive CPAP or Bi-level positive airway pressure therapy.

Study Objectives

The primary objective of the study is to assess patient preference for the Philips Respironics Amara View MCFFM compared to the competitor ResMed AirFit F40 MCFFM. The secondary

Document ID:	N/A	Document title:	Classification:	For internal use
		Clinical Study Protocol		
Modified:	24Jun2024		Author:	[name]
Version:	1.0		Approvers:	[name]/[name]
Status:	Final		Page:	8 of 29

aim of the study is to compare PAP therapy device data between the two masks. A detailed description of the aims is presented in the following table.

Objectives	Hypothesis	Endpoints
To determine patient preference for the Amara View compared to the AirFit F40 as determined by ratings of mask attributes.	Subjective ratings on mask attributes will tend to be higher for the Amara View mask compared to the ratings for the AirFit F40 mask.	
Comparison in satisfaction ratings between the Amara View and the AirFit F40 will be measured for the following attributes:
 
 • Bed partner satisfaction (overall) • Fit (cushion, headgear, frame, mask overall) • Comfort (cushion, headgear, frame, mask overall) • Ability to maintain a seal during use (seal satisfaction, leak location) • Stability of the mask • Noise level (self, bed partner) • Air venting (self, bed partner) • Comfort of breathing • Sleep quality • Visual appeal • Patient Satisfaction overall (headgear, cushion, frame, mask) 
Difference in NPS between the Amara View and the AirFit F40
 
Differences in ease of use and satisfaction ratings between the Amara View and the AirFit F40
 
 • Mask clips • Mask overall • Assembly (elbow, cushion, frame, tubing quick disconnect, mask clips) • Disassembly (elbow, cushion, frame, tubing quick disconnect, mask clips)

Document ID:	N/A	Document title:	Classification:	For internal use

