		Clinical Study Protocol		
Modified:	24Jun2024		Author:	[name]
Version:	1.0		Approvers:	[name]/[name]
Status:	Final		Page:	9 of 29

		
Proportion of patients who prefer the Amara View compared to the AirFit F40 for the following:
 
 • Seal • Comfort • Stability • Noise level • Headgear • Mask cushion attachment ease of use • Less disruptive air venting • Overall preference
Secondary Objective: compare residual AHI values between the Amara View and AirFit F40 masks during PAP therapy.	Residual AHI values will tend not to differ between the Amara View and AirFit F40 masks.	Residual AHI recorded by the participants PAP device while using the Amara View and AirFit F40 masks
Secondary Objective: compare the recorded leak values between the Amara View and ResMed AirFit F40 masks during PAP therapy.	Leak values will tend to be lower for the Amara View mask compared to the AirFit F40 masks.	Leak recorded by the participants PAP device while using the Amara View and AirFit F40 masks.
Secondary Objective: compare the air pressure used during PAP therapy between the Amara View and AirFit F40 masks	Air pressure values will tend not to differ between the Amara View and AirFit F40 masks	Air pressure (cmH20) used during PAP therapy recorded by the participants' PAP device while using the Amara View and AirFit F40 masks
Secondary Objective: compare the adherence to PAP therapy while using the Amara View and AirFit F40 masks	Adherence to PAP will tend not to differ when using the Amara View mask compared to the AirFit F40 mask	Daily hours of use of PAP therapy recorded by the participants' PAP device while using the Amara View and AirFit F40 masks

Data obtained as part of the secondary objectives from this protocol will be used as part of a Post Market Clinical Follow-up Activity.

Document ID:	N/A	Document title:	Classification:	For internal use
		Clinical Study Protocol		
Modified:	24Jun2024		Author:	[name]
Version:	1.0		Approvers:	[name]/[name]
Status:	Final		Page:	10 of 29

Study Design

This is an open-label, randomized cross over trial, comparing patient feedback between the Amara View MCFFM and the AirFit F40 MCFFM. This study will recruit approximately 40 adult patients who are established on PAP or Bi-Level therapy at the time of enrollment.

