Adults who are currently adherent to PAP or Bi-Level therapy will be recruited through sleep clinics. Willing and eligible participants will undertake baseline data collection before using either the Amara View or AirFit F40 masks. Therapy will be delivered using their clinically prescribed PAP or Bi-Level device with no modification to settings.

The study will be completed according to applicable Good Clinical Practices and the Declaration of Helsinki. The study will be monitored onsite and/or remotely, as described below.

Randomization

The order in which participants will use the two masks will be randomized. A fixed allocation permuted-block randomization strategy will be used. Randomization will be administered through the electronic data capture system.

Blinding

There will be no blinding in this trial.

Study Procedures

Recruitment

Participants will be recruited via sleep clinics contracted to recruit participants within the United States. Recruitment may involve a combination of in-person recruitment during clinical appointments, phone calls, and emails. Study staff will be responsible for assessment of inclusion and exclusion criteria (listed below).

Scheduling will be conducted by the site. Participants who are willing to enroll will be scheduled for an in-person visit to provide informed consent and complete study procedures.

Baseline Visit (Visit 1)

Consent, Eligibility and Baseline Information

During the baseline visit, the study site coordinator will review the Informed Consent Form (ICF) with the participant explaining the details of the study and answering any questions the participant may have about the study. If the participant is willing to take part in the study, the ICF will be signed and dated by the participant and the site study representative obtaining consent. A copy of each participant's signed ICF will be given to them for their records.

Those who provide consent will then complete the Demographics Questionnaire (see Appendix I), which collects information about age, gender, sex, race, and ethnicity. Next, they will complete the Baseline Survey (see Appendix II) to collect information about the make and model of their prescribed mask and PAP device. The participants will then complete the Eligibility Questionnaire (see Appendix III) to confirm entry criteria.

Document ID:	N/A	Document title:	Classification:	For internal use
		Clinical Study Protocol		
Modified:	24Jun2024		Author:	[name]

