All variables will be summarized by descriptive statistics. The statistics for continuous variables will include mean, median, standard deviation, minimum, maximum, 95% confidence interval (CI) for the mean, and number of observations. For categorical variables, frequencies and percentages will be presented. All formal analyses will be conducted using SAS®, and statistical comparisons will be considered significant at an alpha of 0.05, with adjustments for multiple comparisons, as applicable. There are no statistical criteria for terminating the study, and any deviations from the original statistical plan will be noted in the analysis report.

Participant Disposition

Participant disposition, including the total number of participants enrolled, randomized, completed and early terminations, will be presented. In addition, a listing will be provided with the reasons for early termination.

Statistical Analyses

Mask attribute ratings, scaled 0-10, will be collected on both the AirFit F40 and the Amara View Full Face masks. Since the study is not statistically powered, the analysis will focus on the effect sizes and confidence intervals of the paired differences between the masks [Amara View – AirFit F40]. The paired t-test and nonparametric Wilcoxon Signed-Ranks test will further evaluate the trends. In cases where one test calculates a p-value below 0.05 and the other indicates a p-value ≥ 0.05 , the distributions of the paired differences will be inspected to determine which method better models the data. Participants will be excluded from the analysis of a given endpoint if they do not contribute a rating for both study masks.

Residual AHI, leak, air pressure, and average adherence will be extracted from the patients' PAP device data, and the paired differences [Amara View – AirFit F40] will be evaluated as described above.

Percentages and exact binomial confidence intervals will be calculated for categorical questions. The McNemar test will compare binary responses where the same questions are answered after the participants try both masks.

Net Promoter Scores (NPS) will be calculated for the question "Would you recommend this (Amara View FFM or AirFit F40) mask to others?" where the percentage of detractors (ratings 0-6) is subtracted from the percentage promoters (ratings of 9 or 10). Ratings of 7-8 will be considered neutral. Relative NPS will be calculated as [Amara View NPS] – [AirFit F40 NPS].

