Document ID:	N/A	Document title:	Classification:	For internal use
		Clinical Study Protocol		
Modified:	24Jun2024		Author:	[name]
Version:	1.0		Approvers:	[name]/[name]
Status:	Final		Page:	21 of 29

Participant Accountability and Missing Data

Participants who withdraw from the study will be tabulated with the reasons for the withdrawal. A participant will only be included in the formal statistical analysis if they contribute data for both study masks.

Safety Analysis

Safety evaluations will be performed by recording adverse events at the time originally reported, and they will be followed at regular intervals until resolution or study completion, whichever comes first. Adverse events will be provided in data listings, but no statistical comparisons will be undertaken.

Interim Analysis

No formal interim analysis is planned for this study.

Exploratory Analyses

Various exploratory analyses may be performed, including subgrouping, correlation, regression, and text analytics, in order to investigate the relation between baseline factors and study endpoints. These analyses could support algorithm development or aid in future study design, but they are not required for the final study report.

Case Report Forms

Study-related case report forms (CRFs) and source documentation will be collected and maintained by the sponsor. All such documentation will be kept confidential and stored on a secure server or protected device. Only staff delegated by the PI will have the ability to enter or make changes to the CRFs and source documents.

Quality Control and Quality Assurance

The PI and study personnel will be trained to the study protocol, study product, TMF documents, monitoring plan, CRFs and/or eCRFs, direct data reporting, and all Sponsor expectations, as applicable. Once complete, training and delegations will be documented for PI and study personnel.

Data queries will be addressed by delegated study personnel, and CRF/ eCRFs will be reviewed and signed off by PI prior to study closure. Monitoring will be completed in accordance with US CFR, ICH-E6 GCP Section 6, and ISO 14155:2011 as applicable and as outlined in the monitoring plan.

Monitoring and Monitoring Plan

Onsite and/or remote monitoring will be conducted for this study. Monitoring details will be outlined in the monitoring plan.

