This clinical study will be monitored by Philips (Sponsor) in compliance with the Code of Federal Regulations (CFR) for clinical research; namely, 21 CFR Parts 50, 54, 56 and 812 and others as applicable. The purpose of such monitoring is to assure that the study remains in compliance with the approved protocol, investigator agreement and regulatory requirements, to verify the

Document ID:	N/A	Document title:	Classification:	For internal use
		Clinical Study Protocol		
Modified:	24Jun2024		Author:	[name]
Version:	1.0		Approvers:	[name]/[name]
Status:	Final		Page:	22 of 29

completeness, reliability and accuracy of study data and to resolve any issues that arise during the conduction of the study. The Sponsor will conduct monitoring visits as specified by the monitoring plan. Monitoring will be conducted by trained clinical research professionals.

It has been determined that this study does not require a Data Safety Monitoring Board (DSMB).

Data Management System

All data will be entered into a 21 CFR Part 11-compliant electronic data capture system (EDC) provided by the Sponsor. The data will be housed within a secure server and accessible only to the sponsor, study personnel, and investigators. Access to the EDC system will be secured through logins managed by a system administrator and appropriate training will be provided. The EDC system provides the capability to perform data management activities within a consistent, auditable, and integrated electronic environment (data security, data entry, data validation). Data entries and modifications will be recorded via an audit trail. If the data manager or study monitors identify data errors or inconsistencies, they will generate queries that will be sent to the Principal Investigators and study staff. After queries are resolved, the database will be locked, and the data will be imported into statistical software and analyzed by biostatisticians.

Deidentified patient data will be retrieved from Care Orchestrator after participants have completed both study arms. Raw data files will be provided to the study team and housed within a server where they will be accessible by the sponsor, study personnel, and investigators.

Protocol Deviations

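### Mask identity is not hidden from the analysts, although the plan leaves the choice of test and any multiplicity adjustment open; coding the masks A and B until those choices are recorded is a cheap improvement

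*Combined protocol and SAP*

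**What the plan says.** - **Blinding.** Study Design describes the trial thus: "This is an open-label, randomized cross over trial, comparing patient feedback between the Amara View MCFFM and the AirFit F40 MCFFM". The Blinding paragraph is one sentence, "There will be no blinding in this trial". It gives no reason and excepts no role.
- **Expected direction.** The hypothesis for the preference objective (Study Objectives table) is "Subjective ratings on mask attributes will tend to be higher for the Amara View mask compared to the ratings for the AirFit F40 mask". The sponsor manufactures the Amara View; the other mask is a competitor's.
- **Endpoints.** Statistical Analyses: "Mask attribute ratings, scaled 0-10, will be collected on both the AirFit F40 and the Amara View Full Face masks". Net promoter scores and stated preferences are added.
- **Open choices.** Both the paired t-test and the Wilcoxon signed-rank test are run. If only one is below 0.05, "the distributions of the paired differences will be inspected to determine which method better models the data". General Considerations applies multiplicity adjustment only where applicable, without naming a method or a family of tests.
- **Survey wording.** The one rating question quoted in the plan is "Would you recommend this (Amara View FFM or AirFit F40) mask to others".
- **Data flow.** EDC data are "accessible only to the sponsor, study personnel, and investigators". After queries are resolved the database is locked and biostatisticians analyse it (Data Management System). The Ethics section codes participants by study number. Nothing codes the masks.

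**The concern.** In a sponsor-versus-competitor comparison of subjective ratings, any analysis decision taken with the data and the mask names both in view can be steered, knowingly or not, towards the sponsor's product. The plan contains one such decision explicitly (which test to believe) and leaves a second unspecified (multiplicity). The participant-level comparison has to be open, but this part does not.

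The study is unpowered and serves mainly as feedback to a design team, which limits the stakes. However, the Ethics and Publication and Registration sections foresee marketing use of the data, where an unmasked analysis of a preference claim is easy to criticise.

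**Working it through.** **Figure to reproduce.** None. The plan states that the study is not powered and gives no effect size, SD or error-rate calculation.

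**Step 1: do the existing guards cover the gap?**

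| Guard | Section | Hides mask identity when choices are made? |
|---|---|---|
| Random mask order | Randomization | No; it balances period |
| Industry-linked people and current users of either mask excluded | Exclusion Criteria | No; it acts on participants |
| Both tests named, deviations reported | Statistical Analyses; General Considerations | No; choosing after inspection is itself the plan |
| Analysis after database lock | Data Management System | No; it fixes the data, not the choices |
| No formal interim analysis | Interim Analysis | No |

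**Step 2: how much can the choice of test matter?** Inputs: 30 pairs (the expected completers, Determination of Sample Size); alpha 0.05 (General Considerations), taken as two-sided because the plan does not say. Assumptions: no true difference, and three shapes for the paired differences. Each was simulated 10,000 times, with zero differences dropped before the Wilcoxon test.

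If the significant test is always taken when the two disagree, the error rate is P(either) = [P(t) + P(W) + P(disagree)] / 2.

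| Paired differences | P(t) | P(W) | P(disagree) | P(either) |
|---|---|---|---|---|
| Normal | 4.97% | 4.92% | 1.71% | (4.97 + 4.92 + 1.71)/2 = 5.80% |
| Normal, SD 2, rounded to whole points | 5.30% | 5.19% | 1.07% | (5.30 + 5.19 + 1.07)/2 = 5.78% |
| Heavy-tailed (t, 3 df) | 4.40% | 4.98% | 2.78% | (4.40 + 4.98 + 2.78)/2 = 6.08% |

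The excess over the larger single-test rate is 0.83, 0.48 and 1.10 percentage points: about 1 point at most.

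**Step 3: the part that depends on knowing the mask.** Suppose the significant test is taken only when the Amara View is ahead, and the non-significant one when it is behind. By symmetry, the error in its favour is P(either)/2 and the error against it is P(both)/2, where P(both) = P(t) + P(W) − P(either).

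- Normal: 5.80/2 = 2.90% in favour; (4.97 + 4.92 − 5.80)/2 = 2.05% against.
- Heavy-tailed: 6.08/2 = 3.04% in favour; (4.40 + 4.98 − 6.08)/2 = 1.65% against.

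A single fixed test at its nominal level gives 2.5% each way.

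**Step 4: what cannot be computed.** The multiplicity choice has no size, because no method or family is named. The effect of brand names in the recommendation item has none either, because the documents give no size of brand prompting.

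**The case against.** The case for leaving the plan alone is reasonable. Open-label is the natural design for a visible product: each mask is fitted in person, taken home with its instructions and used for 15 days, and visual appeal is an endpoint. The analysis emphasises effect sizes and confidence intervals, so p-values are not the main reading. Data are locked first, and the test choice moves error by about one point. All of this stands, and it limits the point to a suggestion.

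Several stronger readings are tempting, but the documents do not support them:

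- **That bias in the ratings is unguarded and could be removed at no cost by taking names out of the questions.** Guards exist, though none removes expectation bias. Neutral wording does not blind someone who has worn both masks. One can calculate that, with 30 pairs and no true difference, an assumed 0.5-point shift and an SD of 2.5 give a significant result favouring the Amara View on 18% of items instead of 2.5%. Both inputs are assumptions, and the changes proposed here would leave most of such a shift in place. That figure shows sensitivity to bias, not a gain from the fix.
- **That staff supply or influence the ratings.** The Case Report Forms section says "Only staff delegated by the PI will have the ability to enter or make changes to the CRFs and source documents", which governs data entry. Visit 2 has participants completing the survey before the second fitting, and the Schedule of Events column covers supervising as well as performing.
- **That the rating questions in general carry brand names.** The appendices are one-line descriptions. Only the recommendation item is shown, and its parenthesis may be shorthand for two versions.

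**Conclusion.** The point holds in a narrow form. No role is masked, nothing codes mask identity for the analysts, and at least one analysis choice is explicitly made after the differences are inspected. The existing guards do not close that gap.

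The measurable size is small. Type I error per endpoint goes from about 5% to about 6% if the significant test is always taken, or from 2.5% to about 3% in the sponsor's favour if the choice follows direction. These figures rest on 30 pairs, two-sided 0.05, no true difference and the three assumed shapes. The multiplicity choice and the brand wording add amounts that the documents do not allow to be computed.

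This is a cheap improvement. It is not evidence that the ratings are biased or that the open-label design is wrong.

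**What to change.** Replace the Blinding sentence with:

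> Participants and site staff are not blinded. The analysis file carries the masks as A and B until the database is locked and all analysis choices (test per endpoint, multiplicity adjustment) are recorded. Staff handling adverse events and the breathing-issue review keep access to mask identity.

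In addition:

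- Word the recommendation item with 'this mask' and no brand names. Leave the Day 30 comparison items clearly labelled: the first mask is due back at Visit 2, and order-only labels there could cause misattribution.
- State participant expectation bias as a limitation in the report.

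Those making the choices should work from the coded file, not the EDC. Coding hides which mask benefits; it does not stop a masked analyst from preferring the significant test, so the reason for each choice should be recorded with it.

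**Cost.** A coded export, a short unmasking step after lock, and small changes to protocol and survey wording. Masking will be imperfect: free-text comments may name the mask, and size data can reveal it, since the Amara View has two headgear sizes and the AirFit F40 three. Such fields can stay out of the coded file until unmasking. No visit, sample size or care is affected.

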After the first 15-day trial period with the first study mask, participants will return to the site for their second study visit. Participants will be instructed to bring their PAP device and return the first study mask to the visit.

Participants will complete a mask attributes survey on the first study mask and then they will be fitted with the second study mask. Fitting procedures will follow the same procedure as described above in the baseline visit. After the mask fitting, participants will be given the second study mask to take home and provided with the Instructions for Use. They will be encouraged to use the mask for the full 15 days of the second trial period. Participants will be instructed to contact the site if they have issues with the recommended cushion and/or headgear size as needed.

If participants did not return the first study mask at the second study visit, they will be asked to bring it to the third study visit.

Document ID:	N/A	Document title:	Classification:	For internal use
		Clinical Study Protocol		
Modified:	24Jun2024		Author:	[name]
Version:	1.0		Approvers:	[name]/[name]
Status:	Final		Page:	12 of 29

It is anticipated the survey completion and mask fitting will take approximately 60 minutes to complete.

Visit 3

After the second 15-day trial period with the second study mask, participants will return to the site for the third and final study visit. During this visit, participants will complete a mask-attributes survey on the second study mask and return all study product.

It is anticipated the survey completion and study product return will take approximately 30 minutes to complete.

After participants have completed both study arms, deidentified data from participants' PAP devices will be extracted from the connected device software Care Orchestrator (CO) for Philips device users only. The site coordinator will confirm the data has been uploaded into CO at visits 2 and 3.

Unscheduled Phone Calls

Documentation of unscheduled phone calls will be captured within the EDC.

Conclusion of Participation

Once the participant returns the study mask(s) and completes the survey, their participation in the study will be complete. Participants will be active in the study for approximately 30 days but no more than 60 days after receipt of the first study mask.

Participant Reimbursement

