Appendix IV Mask Fitting Survey captures the mask (cushion/frame) sizes and fitting observations.

Appendix V Mask Survey – Day 15 is to be administered at 15 days to capture preference, aesthetic appeal, and redness, marks and indentations, etc. for the study mask(s).

Appendix VI Mask Survey –Day 30 is to be administered at 30 days to capture preference, aesthetic appeal, and redness, marks and indentations, etc., and study mask comparisons.

Document Revision History

Version	Date	Author	Description of Change	Reason for Change
1.0	24-Jun-2024	[name]	Initial Release	N/A

Document ID:	N/A	Document title:	Classification:	For internal use
		Clinical Study Protocol		
Modified:	24Jun2024		Author:	[name]
Version:	1.0		Approvers:	[name]/[name]
Status:	Final		Page:	29 of 29

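### The Day 30 mask-to-mask preference items are answered with no planned re-exposure to the first mask, so conditions for the comparison differ between masks and between participants

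*Combined protocol and SAP*

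**What the plan says.** The Study Objectives table lists, as the last group of endpoints under the primary objective: "Proportion of patients who prefer the Amara View compared to the AirFit F40 for the following". Eight items follow: seal, comfort, stability, noise, headgear, ease of cushion attachment, venting and overall preference.

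The Appendices summarise the surveys in one line each. The Day 30 survey (Appendix VI) "is to be administered at 30 days to capture preference, aesthetic appeal, and redness, marks and indentations, etc., and study mask comparisons". The Day 15 summary (Appendix V) also mentions preference but lists no comparison between masks; at that point only one study mask has been worn.

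On handling of the first mask, the Visit 2 section says: "Participants will be instructed to bring their PAP device and return the first study mask to the visit". For anyone who did not do so, "they will be asked to bring it to the third study visit". The Visit 3 section describes a survey on the second mask and the return of study product. It does not mention showing the first mask again.

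The 0-10 attribute ratings are timed differently. At Visit 2, "Participants will complete a mask attributes survey on the first study mask and then they will be fitted with the second study mask"; the second mask is rated at Visit 3. Mask order is randomised in permuted blocks (Randomization). Categorical questions are summarised by percentages with exact binomial confidence intervals, and no summary by sequence or period is mentioned (Statistical Analyses).

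**The concern.** A head-to-head question works best when both products are equally available to the person answering. Here one mask has just been worn and the other is remembered. Headgear and cushion attachment concern physical handling, where having the object present would help most.

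Conditions also vary between participants. Those who return the first mask on time answer from memory, and those who do not may have both masks with them. The setting of the comparison is thus decided by return compliance rather than by design.

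At stake is how faithfully the preference proportions reflect preference. If some respondents fall back on the most recent mask, a real preference is understated. If completers are also unbalanced by sequence, the pooled proportion moves toward the mask more often worn second, and the planned analysis would neither show nor correct this.

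**Working it through.** **Inputs from the protocol.** Visit 2 at Day 15 ± 5 and Visit 3 at Day 30 ± 5 (reimbursement table and Schedule of Events). About 40 enrolled and about 30 completers (Number of Subjects). Randomised order, ratio not stated. Exact binomial intervals and alpha 0.05 (Statistical Methods).

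**Assumptions.** 1:1 allocation; two-sided 95% intervals; a fraction r of respondents, 0 to 30%, names the second mask whatever their true preference. The documents give no value for r or for the true preference p.

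**The plan's own figure.** There is no power calculation to reproduce. The enrolment figures imply a loss of 1 − 30/40 = 25%, and 30/(1 − 0.25) = 40 is consistent with them.

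**Time since the first mask was due back.** Nominal: 30 − 15 = 15 days. Shortest: 25 − 20 = 5. Longest: 35 − 10 = 25.

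**Recency model.** The chance of naming the Amara View is (1 − r)p + r if it was worn second and (1 − r)p if worn first. With q the share of completers who wore it second, the expected pooled proportion is (1 − r)p + rq.

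*Balanced order, no true preference* (p = 0.50, q = 0.5): 0.50(1 − r) + 0.50r = 50% at every r. With 30 completers split 15:15, the chance that the exact interval excludes 50% goes from 4.3% at r = 0 to 3.4% at r = 30%. No false lean is created.

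*Balanced order, assumed true 70%:*

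| r | Expected proportion | Chance the interval excludes 50% (n = 30) |
|---|---|---|
| 0 | 70% | 59% |
| 10% | 0.9 × 0.70 + 0.1 × 0.5 = 68% | 49% |
| 20% | 0.8 × 0.70 + 0.2 × 0.5 = 66% | 40% |
| 30% | 0.7 × 0.70 + 0.3 × 0.5 = 64% | 31% |

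An assumed true 80% at r = 20% becomes 0.8 × 0.80 + 0.2 × 0.5 = 74%.

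*Unbalanced completers, r = 20%, 18:12 by sequence, assumed true 70%:* 0.56 + 0.2 × 0.6 = 68% if the Amara View was more often second, and 0.56 + 0.2 × 0.4 = 64% if less often. That is 2 points either side of the balanced 66%.

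**How likely is such imbalance?** If 30 completers are a random draw from 20:20, a split of 18:12 or worse has probability 6.5% (hypergeometric). This holds only if loss is unrelated to order. The Withdrawal section allows discontinuation when a study mask proves inadequate, so that is not assured.

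**What analysis can and cannot repair.** Averaging the two sequence-specific proportions with equal weight gives (1 − r)p + r/2 whatever the split. With p = 0.50, r = 20% and a 20:10 split, the pooled expectation is 0.40 + 0.2 × 20/30 = 53.3% and the equally weighted one is 50.0%. Dilution remains: an assumed true 70% at r = 20% still gives 66%.

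**Scale.** The exact 95% interval for 15 of 30 is 31% to 69%.

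**The case against.** A head-to-head question cannot be asked until both masks have been worn, and Visit 3 is the earliest visit at which that is so. This stands: the timing of the question is not a fault, and the weak point is only the missing re-exposure.

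A reader might infer that preference is pulled toward the second mask, or that one manufacturer's product is favoured. The documents support neither. They show no recency effect, and every figure for its consequences depends on an assumed r. Randomised order means that a recency effect, if present, favours neither product unless completers are unbalanced by sequence.

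A reader might also infer that the primary objective as a whole is compromised. The objectives table ties it to ratings of mask attributes, and those are taken at the end of each mask's own period. The preference proportions are one of several endpoint groups.

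Nor can it be said that most participants will lack the first mask at Visit 3. The instruction points that way, but no proportion is given. The survey forms appear only as summaries, so item wording, item order and any recall aid cannot be judged.

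Finally, the study is declared unpowered and aimed at directional trends. A dilution of 2 to 6 points at an assumed true 70% is small beside the interval width at 30 completers, and under balanced order the direction is kept. This limits the weight of the point. It does not remove it, because dilution weakens the trend being sought and cannot be undone in the analysis.

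Showing both masks could itself do harm if it came before the second mask's ratings: the first mask was rated before the second had been worn. That objection is sound and governs the order of steps in the fix.

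**Conclusion.** The point holds as a modest, inexpensive improvement to the preference items. The text supports that the mask-to-mask comparison is described only for Day 30, that the first mask is due back at Visit 2 with a fallback to Visit 3, and that no re-exposure is planned. Conditions for the comparison therefore differ between masks and can differ between participants.

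Whether this distorts the answers is unknown. Under the assumed model with balanced order, the cost is dilution toward 50%, with no lean to either product. A shift toward one product requires sequence imbalance among completers; at 18:12 and r = 20% it is 2 points around the balanced value. These sizes rest on the assumed r, the assumed true preference and 1:1 allocation. The 0-10 ratings and NPS are not shown to be affected.

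**What to change.** **Procedure.** In the Visit 2 section, state that the site keeps each participant's returned first mask, bagged and labelled with the study number, until Visit 3. In the Visit 3 section, set this order:

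1. The participant completes the second mask's 0-10 attribute ratings and NPS without the first mask in view. Anyone who brings the first mask to Visit 3 hands it to staff on arrival.
2. The participant is given both of their own study masks to handle and answers the comparison items.
3. Product return and the inventory check follow.

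**Analysis.** Report each preference proportion by randomised sequence, and prespecify the equally weighted average of the two sequences as the summary, with a named interval method for it. This removes any shift from unequal numbers per sequence. It does not remove dilution, or selection if the people lost differ in preference from those who stay.

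**Cost.** A few sentences of protocol text, bagged storage of about 40 masks between visits, and a few more minutes at Visit 3, where an inventory check is already scheduled. Handling the masks in clinic only partly helps memory of overnight seal, noise or comfort, and the documents give no figure for how far it would reduce any recency effect.
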